3.0 Objectives

Objectives:

The primary objective of this study is to implement and evaluate a web-based brief alcohol intervention (BAI) for treating Veterans with HCV and seeking care at two VA liver clinics - Veterans Affairs Palo Alto Health Care System (VAPAHCS) and San Francisco Veterans Affairs Medical Center (SFVAMC). This study will have three aims:

First (**Aim 1**), we plan to assess patient, provider, and system factors that may impact the initial adoption of this intervention in two VA HCV clinics. These data will result in the development of a protocol for the initial implementation of the web-based BAI at our two study sites. A secondary aim will involve obtaining patient and provider feedback on an existing web-based BAI (see www.bmi-aft.org, VA Intranet Only) to help inform its redesign for use with this population.

Second (**Aim 2**), we will implement and examine the effectiveness of a web-based BAI in two liver clinics to reduce alcohol consumption in Veterans with liver disease at three- and six- months post-treatment. Also, a formative evaluation will be conducted to identify potential and actual influences on the progress and effectiveness of the initial implementation efforts that may impact the likelihood that the web-based BAI will be adopted at both sites.

Third (**Aim 3**), we will conduct a budget impact analysis to estimate the short-term costs (1-3 years) of adoption and diffusion of the web-based BAI and the trajectory of health care spending for study participants. We will estimate the budgetary impact from the VA's perspective using a one year time horizon, without discounting. We will use costs of the intervention and the subsequent health spending for participants during their enrollment in the study (six-months) and six- months after enrollment for a total of one year.

Hypotheses:

We anticipate that our study will show that web-based BAIs are a low-cost, effective, and feasible approach for reducing alcohol consumption in VA liver clinics, and by extension could be tried in other care settings as well (e.g., surgery).

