To achieve Aim 3, the budget impact analysis will estimate the costs of adoption and diffusion of the web-based BAI for Veterans with HCV and the trajectory of health care spending for these patients. We will estimate the budgetary impact from the VA's perspective using a one year time horizon, without discounting (Mauskopf et al., 2007). We will estimate the costs of the intervention and the subsequent health spending for participants during their enrollment in the study (six months) and 6 months after enrollment for a total of 1 year. We hypothesize that the BAI intervention will increase utilization of SUD treatment in the first 6 months and then budget neutral from 6-12 months. Savings, if any, would accrue in the 6-12 months after randomization.

With consent, the study will collect the patient's social security number. We will link the social security number to the VA scrambled social security number so that we can extract their VA utilization and cost data. We will collect utilization and cost data from randomization through one year for each participant. Data will be gathered from a variety of sources.

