Part III of the interview will collect data on CFIR domain C - intervention characteristics involved in the care process. Providers will be asked to give their perceptions on current guidelines for treating alcohol use in HCV clinics and availability of treatment options at their facility. For example, potential assessment domains include: (k) perceptions about existing guidelines (e.g., “What do you think about current guidelines for addressing alcohol consumption in your clinic?” and “How effective/ineffective do you feel these guidelines are in helping you address this issue in your patient population?”) and (l) perceptions about and availability of treatment options for alcohol use (e.g., “How do you feel about existing treatment options for your patients reporting active alcohol use?”). In addition, providers will be asked to provide their reactions to the following treatment options: brief physician advice, the VHA brief alcohol counseling performance measure, brief alcohol interventions (e.g., assessment and feedback [BAI]), and referral to specialty SUD care, which (along with responses to questions in Parts I-II) will inform the re-versioning of the web-based BAI.

Aim 2

Veteran participants will be randomized into the experimental condition or TAU. Participants in the experimental condition will receive a web-based BAI which follows the general approach that has proven to be effective in previous studies. The BAI consists of two components (a) a brief computerized assessment and (b) a personalized feedback report (also see section 5.1).

All participants will receive an assessment at baseline, and follow up at 3- and 6-months. The assessment consists of the following topics: demographics, liver disorder diagnosis and treatment eligibility, patient satisfaction, primary and secondary outcomes.

Assessment Instruments

(a) Demographics. Characteristic such as age, gender, and previous or current involvement with inpatient/outpatient VA (or non-VA) substance use disorder (SUD) treatment or mental health care programs will be collected from the patient and through administrative records (CPRS and CDW). We will also assess current (or past) participation in a self-help SUD program such as Alcoholics Anonymous. We will assess possible exposure to these various forms of substance abuse treatment during the three- and six-month follow up periods.

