Prior to any regression modeling, we will first examine the sample distributions of each outcome variable and predictor variable to help us identify any possible errors in the data (e.g. coding errors). One of the benefits of our proposed use of generalized linear mixed model (GLMM) regression analyses is that it can accommodate a variety of conditional distributions for each outcome variable. Given that we will randomly assign participants to each condition, we expect the two groups to be comparable on baseline demographics and outcome variables at baseline. Nevertheless, we will conduct independent groups t-tests or chi-square analyses to check for any differences between the two groups on demographic characteristics and baseline outcome assessments. If differences are found between groups on any variables, we will control for those variables in subsequent analyses. Next, we will use generalized linear mixed-model (GLMM) regression analyses to compare the two conditions on our primary and secondary outcomes (Raudenbush et al., 2001; Singer et al., 2003). The primary hypothesis is that the slope of drinking outcomes over 0 to 6 months for participants in the web-based BAI plus TAU condition will differ from the TAU only condition. We will use the repeated measures data to fit a model consisting of fixed-effect terms for time since randomization, the time by condition interaction, and the site main effect. Random intercepts will be included to account for possible correlation among repeated measurements due to patient-specific latent factors. We will examine further constraints on the covariance structure and choose the final model by assessing goodness-of-fit. We will also examine the distribution of the outcome variables and associated random error components, choose appropriate link and variance functions (McCullagh & Nelder, 1991), and review any outliers.

Examining Mediators and Moderators

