As described above, we will estimate the average cost of the intervention. For each participant, we will summarize their utilization and cost data. We will then perform a budget impact analysis of the intervention, comparing all health care costs for each arm of the study, including the costs of the intervention (e.g. providing the web-based BAI). Consistent with guidelines (Mauskopf et al., 2007), we will not include costs of developing the intervention or administrative overhead. Assuming also, that the BAI may impact both immediate decisions about alcohol use as well as decisions about other health care in the near future, we will analyze all health care utilization and costs incurred within the 12 months following randomization. We will also compare costs incurred in the first 6 months to those incurred in the second six months. We will estimate the budgetary impact for the two sites involved with the study. We will then extrapolate from these sites to create projections for other VAMCs based on the prevalence of patients with HCV and alcohol use at each site. This will allow us to estimate the budget impact of diffusing the web-based BAI throughout the VA system. Economics data will be managed in the same way as the clinical data and housed at HERC. We will adopt the same procedures and policies developed in the Aim 2.

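### Aim 3 extracts cost data only from randomization onward; adding the prior year would be a cheap gain in precision and would give the spending trajectory a pre-enrolment level

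*Combined protocol and SAP*

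**What the plan says.** Section 5.1 (Aim 3) sets the data window: "We will collect utilization and cost data from randomization through one year for each participant". The same sentence stands under Aim 3 in sections 5.2 and 5.5.

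Section 5.6 (Aim 3) keeps to that window: "we will analyze all health care utilization and costs incurred within the 12 months following randomization". The arm comparison is described as "comparing all health care costs for each arm of the study, including the costs of the intervention", and the time comparison as "We will also compare costs incurred in the first 6 months to those incurred in the second six months". No model, covariate, test or interval is stated for costs.

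The aim itself includes "the trajectory of health care spending for study participants" (section 3.0), and section 5.1 likewise refers to "the trajectory of health care spending for these patients". The only time points planned for it are the two half-years after randomization.

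Two other places come near to baseline cost without supplying it:

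- Section 5.5, under Demographics, says that "previous or current involvement with inpatient/outpatient VA (or non-VA) substance use disorder (SUD) treatment or mental health care programs will be collected". The sources are self-report and administrative records. That is involvement in two types of care, not spending.
- Section 5.6 (Aim 2) says "If differences are found between groups on any variables, we will control for those variables in subsequent analyses". The rule sits with the models for the Aim 2 outcomes and refers to demographics and baseline outcome assessments. It cannot reach a variable that is never extracted.

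**The concern.** Each drinking outcome in Aim 2 has a baseline value, and the sample size calculation relies on a correlation between repeated measures. Cost, which comes from existing records and needs no patient contact, has no baseline value. Two things are lost.

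**Precision.** The trial was sized for drinking outcomes, and Aim 3 has no precision target of its own. If a participant's earlier spending predicts later spending, adjusting for it removes part of the person-to-person variation from the arm difference. The arm estimates also feed the projection to other VA medical centers, so their relative uncertainty is carried into it.

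**Interpretation of the trajectory.** Two half-years, both after randomization, show how spending moves within the study year and how the arms differ. They cannot show whether spending rose or fell from its level before enrolment.

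**Working it through.** **1. The plan's own figure.** Aim 3 states no cost SD, effect, precision or sample size, so there is no cost figure to reproduce. It uses the Aim 2 participants, 170 per arm. The Aim 2 inputs (effect size .35, 80% power, two-sided .05, 20% attrition) give:

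- n = 2(1.960 + 0.842)²/0.35² = 128.2, so 129 per arm
- 129/0.80 = 161.3, so 162 per arm

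The stated 170 is slightly more than its inputs require and has no bearing on the cost question. The 20% attrition concerns telephone follow-up. Costs come from administrative files, so up to 170 per arm may be available.

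**2. Unadjusted precision.** The 95% half-width for a difference in mean cost is 1.96 × √(2/170) = 0.213 SD. The documents give no cost SD. If the SD is assumed to be 2 to 3 times the mean (CV 2 to 3), this is 42.5% to 63.8% of mean cost.

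**3. Effect of adjusting for prior cost.** With correlation r between prior and later cost, the width is multiplied by √(1 − r²). The unadjusted sample that gives the same precision is 170/(1 − r²) per arm. The documents do not give r, so a range is shown.

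| Assumed r | Width factor | Narrowing | Half-width, CV 2 | Half-width, CV 3 | Equivalent n per arm |
|---|---|---|---|---|---|
| none | 1 | – | 42.5% | 63.8% | 170 |
| .1 | 0.995 | 0.5% | 42.3% | 63.5% | 172 |
| .3 | 0.954 | 4.6% | 40.6% | 60.8% | 187 |
| .5 | 0.866 | 13.4% | 36.8% | 55.2% | 227 |
| .7 | 0.714 | 28.6% | 30.4% | 45.5% | 333 |

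**4. Check with skewed costs.** The simulation used lognormal costs with CV 2, 170 per arm and 2,000 runs. Adjusting for untransformed prior cost, the SD of the estimated arm difference fell to 0.94, 0.82 and 0.64 of the unadjusted value at r = .3, .5 and .7. Adjusting for the logarithm of prior cost gave 0.95, 0.91 and 0.84. All estimators averaged close to the true difference of zero. So there is no bias either way, and the gain depends on the form of the covariate as well as on r.

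**5. Which part of the range is plausible.** For lognormal costs with log-scale variance s² = ln(1 + CV²) and log-scale correlation g, the correlation on the dollar scale is (exp(g·s²) − 1)/CV². With g = .5:

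- CV 2: s² = ln 5 = 1.609, so r = (2.236 − 1)/4 = .31, a narrowing of about 5%
- CV 3: s² = ln 10 = 2.303, so r = (3.162 − 1)/9 = .24, a narrowing of about 3%

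A dollar-scale r of .5 at CV 2 needs g = ln 3/ln 5 = .68. An r of .7 at CV 3 needs g = ln 7.3/ln 10 = .86. Under strong skew, the larger gains therefore require a strong log-scale correlation.

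**The case against.** The case for leaving the plan as it is has several parts.

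- *The comparison is valid already.* This stands. Chance differences between arms in prior spending are ordinary sampling error. A reader might infer that the missing baseline biases the cost comparison; randomization rules that out.
- *The plan does not commit to an unadjusted analysis.* This also stands. Section 5.6 states no interval and does not rule out covariates. The statement about width therefore applies to any interval later computed. But prior cost cannot be used later if it has not been extracted.
- *The Aim 3 hypotheses need no pre-period.* Correct. More SUD treatment use in months 0 to 6 and budget neutrality in months 6 to 12 can both be judged against the TAU arm. What cannot be shown is change from before enrolment.
- *A before-and-after picture could mislead.* Section 5.2 recruits some patients by letter after a visit in the prior week, so cost just before enrolment may be raised. This is a reason to report the earlier periods by arm and with a caveat, not a reason to omit them.
- *Prior SUD spending is restricted by design*, because patients currently in SUD treatment are excluded. This limits how well prior cost predicts the component most likely to change. Section 5.6, however, compares all health care costs.
- *Feasibility is not established.* Partly right. The data are a subset contributed by OMHO (section 5.5) with no stated look-back, and the permission in section 5.3 is described only as use of the social security number. Both need confirming.

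**Conclusion.** The point holds as a cheap improvement. The Aim 3 window excludes prior cost, and neither the baseline record of SUD and mental health care nor the Aim 2 adjustment rule replaces it. The cost is some precision and the pre-enrolment reference level for the trajectory. The second loss does not depend on any assumed correlation.

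The gain in precision runs from negligible (0.5% at r = .1) to substantial (29% at r = .7). It rests wholly on a correlation that the documents do not give, and with highly skewed costs a gain of about 3% to 5% is quite possible.

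Three stronger readings are tempting and not supported:

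- That the trial forgoes the equivalent of 33% to 96% more patients. This is 1/(1 − r²) − 1 at r = .5 and .7, the favourable end of the range.
- That extrapolation to the VA system magnifies the noise. Scaling multiplies the estimate and its standard error alike, so relative precision is unchanged.
- That adjustment would protect against a few high-cost patients deciding the result. It helps only where those patients were already costly before randomization.

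**What to change.** 1. **Sections 5.1, 5.2 and 5.5 (Aim 3).** Extend the extract to run from 12 months before through 12 months after randomization, with the same cost categories in both periods, including Fee Basis care. First confirm that consent and the OMHO data-use permission cover the earlier period.
2. **Section 5.6 (Aim 3).** Prespecify the arm difference in 12-month cost, adjusted for prior 12-month cost and the randomization strata (site and alcohol dependence). State the form in which prior cost enters, and give a 95% interval suited to skewed costs, such as a bootstrap interval.
3. **Trajectory.** Report the two half-years before and the two after randomization by arm. Treat the earlier two as descriptive, and note that recruitment after a recent visit may raise cost just before enrolment.

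The cost is a longer date range in an extract already planned, one covariate and the permission check. The identifier link and the source files are already in the plan, and no visit, patient contact or enrolment is added. If the permissions do not cover the prior year, the planned comparison remains valid. Section 5.6 should then say that the trajectory starts at randomization.

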5.2 Recruitment Methods

Aim 1

Interviews will be conducted, over the telephone, with patients (N= 30, 15 per site) and providers (N = 10, 5 per site). A rolling recruitment strategy will be used resulting in one-on-one phone interviews until enrollment is complete. Patient participants will be recruited by responding to a study flyer provided to them by their HCV clinic provider, or posted in an exam room or clinic research bulletin board. Patients may then contact us directly by a phone number listed on the study flyer. Veterans will be screened for eligibility by the study coordinators when they call in or are referred by an HCV clinic provider, and those eligible will schedule a phone interview with the research staff. Patients with evidence of active psychosis, dementia, and/or terminal illness will be ineligible to participate. Patient participants will be reimbursed \$50 for their participation.

All providers working in the HCV clinics at each site will be eligible to participate in 30 minute interviews conducted over the telephone. An interdisciplinary group of 10 providers (10 at each clinic) work at each of the two HCV clinics included in our study. We will focus our efforts on recruiting a minimum of 5 providers at each site including physicians, clinic nurses (RN, LVN), and mental health staff given their involvement at different points in the screening

and intervention process. For example, within the HCV clinic setting at the Palo Alto Division of the VAPAHCS, nurses and physicians assistants are typically involved in the initial screening of alcohol use, while the mental health staff is often responsible for more in depth assessment of alcohol use, counseling, and referral. At both sites, provider participants will be recruited through clinic monthly meetings. The study coordinators, with the support of clinic Directors, will provide a short presentation on the study during clinic monthly meetings to invite providers to participate. Study coordinators will contact interested providers to schedule a thirty-minute, one-on-one semi-structured interview over the phone that will be conducted by the study coordinator. Participating clinics will be offered their choice of text books published by the American College of Physicians as a continuing medical education tool in recognition of their participation.

Aim 2

We estimate that we will need 170 individuals per condition at baseline for a total sample of 340 across both sites, with one half in the experimental condition and TAU condition at each site (i.e., n=85 per condition at Palo Alto, n=85 per condition at San Francisco).

Veterans will be recruited through provider referral, flyers posted in both liver study clinics, and through the use of administrative records (CPRS and CDW) at both sites. The PI and Co-Is will educate providers at each site about the study in their monthly meetings. Study staff will present a brief overview of the study objectives, criteria for Veteran participant eligibility, and low-response options (e.g., contacting study staff within clinic) for referring potential participants to the study. The research team will also provide flyers describing the study (e.g., describing participant eligibility and study team contact information) throughout each of the study clinics. We will place flyers in exam rooms, waiting rooms, and at clinic check-in desks. We will also provide flyers to clinic staff (e.g., nurses and mental health staff) to be given to eligible patients during the exam and subsequent psychosocial assessment.

Finally, in collaboration with our Co-Is, participants will also be recruited through the use of administrative records obtained through CPRS and CDW. Specifically, we plan to identify patients who have completed a scheduled visit during the prior week and mail them a letter (signed by the clinic director for that site) describing the study, eligibility criteria, and a phone number for contacting study staff.

Our research team has extensive experience using these recruitment strategies to good effect. For example, study Co-Principal Investigator [name] is currently conducting an HSR&D funded randomized clinical trial in a VA primary care clinic examining the effect of a web-based BAI on alcohol consumption among Veterans with alcohol misuse. His study is utilizing the above recruitment strategy with excellent results. For example, his [MC] study (n = 160 to date) currently has an 80% recruitment rate among eligible participants, and an 85-90% three- and six-month follow up rate ([name] et al., 2011). We will also take advantage of and utilize recruitment and retention strategies that are well-established among HSR&D investigators at the Center for Health Care Evaluation for use in the present study.

Patients agreeing to participate will be asked to complete an assessment at baseline and again at three- and six-months post-treatment. Baseline interviews will be conducted in person by study staff, with both follow-up assessments conducted via telephone. Participants will be reimbursed \$50 (for a possible total of \$100) for their participation after completion of the baseline assessment, and \$25 each for the phone assessments.

Aim 3

With consent, the study will collect the patients' social security number. We will link the social security number to the VA scrambled social security number so that we can extract their

VA utilization and cost data. We will collect utilization and cost data from randomization through one year for each participant. Data will be gathered from a variety of sources.

5.3 Informed Consent Procedures

Aim 1

Informed consent will be obtained verbally over the phone by the study coordinators when patients/providers call our study team in response to a study flyer. We will request a Waiver of Documentation of Informed Consent to obtain permission from patients and providers to participate in the study and to consent to audiotaping. Informed consent will be obtained before interviews are conducted by our study staff. Patients with evidence of active psychosis, dementia, and/or terminal illness will be ineligible to participate.

Aim 2

Informed consent will be obtained in written form by the study coordinators when patients are identified as possible candidates. Patients of the liver clinic indicating any use of alcohol in the prior 30-day period will be recruited to participate in this study. To enhance the generalizability of our findings, we are only excluding Veterans who are currently enrolled in an outpatient or inpatient substance abuse program. Veteran participants currently seeking other mental health care treatment will be included in this study and the details of this care will be well documented in the baseline assessment process. This will allow us to examine whether this factor moderates the effect of the study conditions on patient outcomes. Also, patients with evidence of active psychosis, dementia, and/or terminal illness will be ineligible to participate.

Aim 3

Participants who provide informed consent for Aim 2 will also be asked for permission to use their social security numbers, which addresses data access for Aim 3.

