To address Aim 1, we will conduct qualitative semi-structured interviews with Veterans and clinic staff at both sites to achieve two objectives: (a) identify patient, provider, and system factors that serve as potential facilitators or barriers to the initial adoption of a web-based BAI as an intervention for reducing alcohol consumption, and (b) obtain patient and provider feedback on the content and presentation of a web-based BAI to help inform its redesign for use with Veterans with HCV and consuming any level of alcohol. Re-versioning the existing intervention will increase its usefulness and adoptability among HCV providers and patients with HCV by enhancing its relevance to the specific health needs of this population. Interviews with providers and patients will be conducted over the phone.

Risks and Benefits

There are no anticipated risks associated with participation in Aim 1 of this study. However, interviews may involve risks that are currently unforeseeable. For example, it is possible that participants may experience some discomfort answering some of the questions. The benefits which may reasonably be expected to result from this study include providing the scientific community with information on HCV care and the utility of BAI in HCV clinics.

Study Population

Study coordinators at both sites will conduct semi-structured (audio-recorded) interviews, over the telephone, with both patient (N = 30, 15 per site) and provider (N=10, 5 per site) participants to help inform both the initial implementation and the re-versioning of the web-based BAI for two VA HCV clinics. Patients will include men and women veterans who have been diagnosed with HCV, attend the HCV clinic at VAPAHCS or SFVAMC, and are currently using any level of alcohol. Patients with evidence of active psychosis, dementia, and/or terminal illness will be ineligible to participate. Providers from HCV clinics at VAPAHCS or SFVAMC will be eligible to participate.

Aim 2 (Years 2-3)

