5.4 Inclusion/Exclusion Criteria

The study sample will be drawn from a population of Veterans who currently receive VA services and providers in two VA Liver Clinics. Veterans presenting to HCV clinics who report engaging in any level of alcohol use within the prior 30 days will be recruited for the study.

Additional criteria for inclusion include: (a) a liver disease diagnosis, (b) not presently in treatment for a substance use disorder, and (c) no evidence of active psychosis, dementia, and/or terminal illness. Any provider responsible for direct patient care at either study site Liver Clinic will be eligible to participate in Aim 1.

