Part II will collect information on CFIR domain B - the characteristics of individuals involved in the care process. Questions in this domain will assess patient and provider characteristics that may influence HCV patients’ willingness to discuss their alcohol use and receive care when appropriate. Example questions will focus on such factors as (e) communication (e.g., “Are there ways in which your provider talks to you that affects/influences your willingness to discuss alcohol use?”); (f) awareness of the consequences of drinking (e.g., “What do you know about alcohol’s effect on your health?”); (g) importance of feedback (e.g., “What type of feedback is (or was) most influential in understanding the health effects of drinking?”); (h) decision to change (e.g., “To what extent does changing your eligibility for antiviral treatment impact your interest in seeking care for your alcohol use?”); and (i) readiness to use a web-based BAI (e.g., “Describe your degree of openness to interacting with a BAI delivered by the internet.”, “What factors influence your interest/willingness to interact with a self-administered BAI?”).

Part III will focus on CFIR domain C - intervention characteristics involved in the care process. Patient participants will be presented content from several evidence-based approaches for addressing alcohol use including: (a) brief advice, (b) brief alcohol counseling (e.g., VHA brief alcohol counseling performance measure), (c) brief alcohol interventions (e.g., assessment and feedback [BAI]), and (d) referral to specialty SUD care. Patient participants will be asked for feedback and reactions to the content of these care strategies, their format, and general presentation. If participants have been exposed to these approaches before in their interactions with providers, they will be asked for their reactions to and experiences with them. Patient feedback on these care strategies (and responses to questions in Parts I-II) will be used to help inform the re-versioning of the web-based BAI. For example, these interviews may yield rich information regarding patient preferences on types of specialty SUD programs (e.g., outpatient mental health) and approaches to the referral process (e.g., direct provider prescription, preference for the “hallway handoff”) that will inform the manner in which we integrate this information into the web-based BAI.

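### The Aim 2 criteria do not exclude the up to 30 Aim 1 patient interviewees, who have already been presented with BAI content; one eligibility line would close the gap

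*Combined protocol and SAP*

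**What the plan says.** **Aim 1.** Section 5.1 (Aim 1, Year 1) plans telephone interviews with 30 patients, 15 per site: "Patients will include men and women veterans who have been diagnosed with HCV, attend the HCV clinic at VAPAHCS or SFVAMC". They must be drinking at the time. One of the two objectives is to "obtain patient and provider feedback on the content and presentation of a web-based BAI to help inform its redesign". Section 5.5 (Aim 1, Part III) describes the exposure: "Patient participants will be presented content from several evidence-based approaches for addressing alcohol use including" brief advice, brief counselling, assessment-and-feedback BAI, and referral to specialty care.

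**Aim 2.** Section 5.1 (Aim 2, Years 2-3) randomises 340 Veterans at the Palo Alto and San Francisco liver clinics. They need a liver diagnosis and some drinking in the past 30 days. The remaining criteria in section 5.4 are "not presently in treatment for a substance use disorder, and (c) no evidence of active psychosis, dementia, and/or terminal illness". Section 5.1 gives the same list, and section 5.3 states "we are only excluding Veterans who are currently enrolled in an outpatient or inpatient substance abuse program" before adding the psychiatric, cognitive and terminal-illness exclusions. None of the three places mentions Aim 1.

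**Measurement and analysis.** The section 5.5 baseline battery asks about earlier substance use treatment, mental health care and self-help groups, but not about the Aim 1 interview. The section 5.6 model has terms for time, time by condition and site, plus any demographic or baseline outcome variable found to differ between arms. Aim 1 participation is not among them.

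**The concern.** Both aims draw on the same clinics, and both use flyers and provider referral. A patient interviewed in Year 1 can meet the Aim 2 criteria in Years 2-3. Two consequences are possible.

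- A TAU-only participant may already have seen and discussed BAI content. The arms would then differ less than intended in that patient, and neither participants nor staff are blinded.
- A BAI-arm participant may have helped redesign the tool. This matters most for the H2 outcomes of satisfaction and knowledge, where ratings from people who shaped the content are not an independent test of it.

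Because participation is not recorded, the trial could neither detect the overlap nor examine its effect afterwards.

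**Working it through.** **Who could overlap.** Aim 1 and Aim 2 share the two clinics and the requirement of current drinking, and an HCV diagnosis satisfies the Aim 2 liver criterion. Aim 1 does not exclude patients in substance use treatment, but Aim 2 does. The ceiling is therefore 30 of 340 = 8.8%, or about 15 per arm under 1:1 allocation. The eligible number is lower by those who have stopped drinking, no longer attend or are in treatment.

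**Inputs (section 5.6, Aim 2).** Effect size .35, power 80%, two-sided alpha .05, correlation .5, attrition 20%, 170 per arm.

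**The plan's own figure.**
- With correlation .5, the change-score variance in SD units is 2(1 − .5) = 1. The 0/3/6-month slope, scaled to six months under compound symmetry, has the same variance: 36 × .5 / 18 = 1.
- n per arm = 2(1.960 + 0.842)² / .35² = 128.1, so 129 completers.
- 129 / .80 = 161.3, so 162 at baseline (163 with the exact t-test). The plan states 170, which is slightly conservative.
- Adding the 5% item-level missingness mentioned later in section 5.6 gives 129 / (.80 × .95) = 169.7, so 170. The plan does not say that it did this.

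**Power as planned.** Completers per arm = .80 × 170 = 136. Power = Φ(d√(n/2) − 1.960) = Φ(.35 × √68 − 1.960) = Φ(0.926) = 82.3% (t-test 82.0%).

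**Effect of overlap.** Let k be the interviewees enrolled, spread evenly over the arms, and r the share of the BAI-versus-TAU contrast that remains in them. Then d = .35 × [1 − (k/340)(1 − r)]. The documents give neither k nor r, so the values below are assumptions.

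| k enrolled | d (r = 0) | Power (r = 0) | d (r = .5) | Power (r = .5) |
|---|---|---|---|---|
| 0 | .350 | 82.3% | .350 | 82.3% |
| 5 | .345 | 81.2% | .347 | 81.7% |
| 10 | .340 | 80.0% | .345 | 81.2% |
| 15 | .335 | 78.8% | .342 | 80.6% |
| 20 | .329 | 77.5% | .340 | 80.0% |
| 30 | .319 | 74.9% | .335 | 78.8% |

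The exact t-test is about 0.3 points lower throughout (for example 79.7% at k = 10, r = 0, and 74.6% at k = 30, r = 0).

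**Sensitivity to the planning basis.** If the 5% item-level loss is also taken, leaving 129 analysable per arm, power is about 80% with no overlap and about 73% in the extreme case. If the true effect is .375, the middle of the .35 to .40 average range in section 5.6, the extreme case on 136 per arm still gives about 80%. At .40 it gives about 85%.

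**The case against.** The strongest reply is that the Aim 1 exposure is not the intervention. Section 5.1 defines the BAI as a computerized assessment of the patient's own drinking followed by an individualized report. Aim 1 is a telephone interview about content from four approaches, after which the tool is re-versioned. No interviewee is described as entering data or receiving a report. Zero remaining contrast (r = 0) is therefore a worst case. This stands.

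Second, the exposure comes before the Aim 2 baseline. Section 5.6 compares slopes from 0 to 6 months, and section 5.5 compares follow-up drinking with baseline. A lasting effect of the interview would already sit in the baseline level. To narrow the contrast it must alter change after randomisation. In the BAI arm, earlier exposure could weaken the response or reinforce it. This also stands. Dilution is a possibility, and its direction is reasonably clear only for a TAU participant who changes because of what was seen.

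Third, section 5.3 keeps exclusions few for the sake of generalizability. That is a sound aim, but leaving out at most 30 people who helped develop the tool hardly affects it.

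A reader might go further and infer three things that the documents do not support:
- **That the BAI effect is diluted, as a fact.** Neither the number who would enrol nor the effect of the interview is given.
- **That every interviewee who still drinks is eligible.** Those in substance use treatment at Aim 2 screening are already excluded.
- **That participants in the primary-care study cited in section 5.2, a "randomized clinical trial in a VA primary care clinic examining the effect of a web-based BAI on alcohol consumption among Veterans", are a further source of contamination.** The plan cites it for recruitment experience and states neither shared patients nor a shared tool.

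**Conclusion.** The gap is real and small. No Aim 2 criterion excludes Aim 1 patient interviewees, and their participation is neither recorded nor modelled. At most 8.8% of the sample could be affected, and probably fewer. With 136 completers per arm and an effect of .35, it takes about 10 enrolled interviewees with no contrast left, or about 20 with half the contrast left, to bring power from 82% to the planned 80%. The 75% figure needs all 30 to enrol and the contrast in them to be zero. These results rest on even allocation and on assumed values of k and r. Randomisation spreads such patients over both arms by chance, so no bias in favour of the BAI follows on the drinking outcomes. What the power figures do not capture is the loss of independence on satisfaction and knowledge. This is a cheap improvement to the design and not a threat to its validity.

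**What to change.** Add to the Aim 2 criteria in sections 5.1, 5.3 and 5.4: Veterans who took part in the Aim 1 patient interviews are not eligible for Aim 2. Check this with one screening question and against the coordinators' Aim 1 enrolment records. The plan does not describe an Aim 1 log, and Aim 1 consent is verbal, so confirm that a usable list exists. If it does not, the screening question carries the check.

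If the sponsor prefers to keep eligibility as it is, record Aim 1 participation at baseline and pre-specify a sensitivity analysis of the primary and H2 outcomes without those patients. Exclusion has to be settled before randomisation starts.

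The cost is at most 30 fewer candidates, from a pool that section 5.1 expects to be large enough, and a slightly narrower eligible population. The sample size does not change. No exclusion is needed for the primary-care trial on the information given.
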